### 4.2.1 PRIMARY ENDPOINT

Self-reported pain will be obtained from all study subjects using the Numeric Pain Rating Scale to score the subject's pain on a 0 to 10 scale. This scale has been validated and widely used. A pain level will be assessed with enrollment in order to assure the participant has pain. An additional assessment will take place at the first visit (day 0). Pain will then be ascertained daily (including during the "washout" period between the two intervention periods) through a daily pain log kept by participants. The pain logs will be requested from participants at each follow-up visit and at the end of each month in the treatment periods, and data from the pain logs will be compiled and analyzed

at the start and end of each of the two treatment periods (on days 0, 90, 120, and 210). Monthly pain averages will be compared to baseline.

The primary endpoint will be change in pain score between baseline and monthly average pain scores. The pain score on each day of month one will be averaged to obtain the average pain score for month one, and the same will be done for months two and three, and each of the monthly average scores for resveratrol and placebo periods will be compared to baseline.

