## 10.2 STATISTICAL HYPOTHESES

The primary hypothesis is that patients' report of pain (and/or use of pain medication) will be 2.8 points lower on the pain scale (0-10) while on the resveratrol than while on placebo.

The secondary hypothesis for this study states that the change in self-reported HRQoL from the start of the study period to the end will be different in PSACH patients during the period they are on resveratrol compared to when they are on placebo.

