### 10.4.2 ANALYSIS OF THE PRIMARY EFFICACY ENDPOINT(S)

A baseline pain assessment will take place at the first visit (day 0). Pain will then be ascertained daily (including during the "washout" period between the two intervention periods) through a daily pain log kept by participants. The pain logs will be requested from participants at each follow-up visit and at the end of each month in the treatment periods, and data from the pain logs will be compiled and analyzed at the start and end of each of the two treatment periods (on days 0, 90, 120, and 210). Each of these scores will then be entered as raw values for each subject if the parameter distribution is non-normal, ranked values will be used as units of analysis.

The primary endpoint will be change in pain score between baseline and monthly average pain score. The pain score on each day of month one will averaged to obtain the average pain score for month one, and the same will be done

for months two and three, and each of the monthly average scores for resveratrol and placebo periods will be compared to baseline.

In an extreme condition, if a sufficiently large proportion (>30%) of the study subjects experience no pain (a score of 0), zero-inflated negative binomial models will be utilized to analyze the data while considering the individuals that report no pain.

---

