### 10.5 SAMPLE SIZE

Although studies haven't quantified pain variability in PSACH, other studies have utilized a pain VAS and have reported standard deviation (SD) of the difference between scores for the same patient of about 10-15 on a 1-100 scale. In addition, previous research by one of the investigators has suggested that a strong placebo effect can be present in studies using the pain VAS at a magnitude of about 20 on a 1-100 scale. Assuming a similar degree of variability in our study population and considering the placebo effect as reported, with a sample size of 30 participants at a Type I error rate of 5%, the minimal detectable difference would be 2.8 units at a SD of 10 and power of 80%, 4.25 at a SD of 15 and power of 80%, 3.3 at a SD of 10 and power of 90%, and 4.9 at a SD of 15 and power of 90%. Considering that there are about 300 potential patients that can be approached through the "Little People of America" support group and the Facebook PSACH group, we should be able to recruit into the study at least half of those highly motivated and invested individuals. We should be able to achieve our sample size of 30 patients for this study, even assuming a considerably high 33% attrition rate. We will screen 60 to enroll 30.

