#### 10.6.1 ENROLLMENT/ RANDOMIZATION/ MASKING PROCEDURES

One hundred individuals with PSACH will be enrolled in the study and then randomized to receiving resveratrol or placebo first based on randomization assignment by biostatistician. We will not replace enrollees that drop out as we have statistical power to lose 10% of the cohort and still determine whether the supplement provides relief of pain. All study participants will be blinded to the study drug. All study investigators and analysts will be blinded to the study drug with the exception of the study coordinator who will be responsible for mailing out the study medications.

---

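### The zero-inflated negative binomial fallback does not fit the primary endpoint, and the rank fallback has no defined trigger and gives no difference in points

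*Combined protocol and SAP*

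**What the plan says.** Section 4.2.1 defines the outcome: "The primary endpoint will be change in pain score between baseline and monthly average pain scores". Daily 0-10 scores are averaged within each treatment month, and each average is compared with baseline. Section 10.4.2 repeats this definition.

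Section 10.2 states the primary hypothesis on the same scale: pain "will be 2.8 points lower on the pain scale (0-10) while on the resveratrol than while on placebo". Section 10.1 treats a difference of 2 units or more as a true change. Section 10.5 sizes the trial on a mean difference, using a "standard deviation (SD) of the difference between scores for the same patient of about 10-15 on a 1-100 scale".

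Section 10.4.1 names multilevel mixed-effects models as the general approach. Section 10.4.2 then adds two conditional branches:
- Scores are entered raw, but "if the parameter distribution is non-normal, ranked values will be used as units of analysis".
- In what the section calls an extreme case, when more than 30% of participants have a score of 0, "zero-inflated negative binomial models will be utilized to analyze the data while considering the individuals that report no pain".

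The section does not say which test, threshold or variable decides non-normality. It does not say on which day, month or period a score of 0 is counted, which branch prevails if both apply, or how a rank or count-model result is turned back into points.

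**The concern.** The hypothesis, the threshold for a true change and the sample size are all expressed as a difference in pain score. The primary analysis therefore has to return that quantity. Both fallbacks move away from it.

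The count model is the clearer problem, because its likelihood does not exist for the values that the endpoint takes. If the trigger were met, the analyst could not follow the plan and would have to improvise a different outcome or a different model. The rank branch can be run, but two competent analysts could disagree on whether it applies, and its estimate is not in points. What is at stake is whether the primary result answers the stated hypothesis, and whether the analysis is fixed tightly enough to be reproduced.

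**Working it through.** **The plan's own figure.** The plan gives no calculation for either branch. Its relevant figure is the 2.8 in sections 10.2 and 10.5. With a two-sided 5% error rate (sidedness is not stated) and a paired difference, the minimal detectable difference is SD × (1.96 + 0.84)/√N.
- "with a sample size of 30 participants" and SD 10: 10 × 2.80/√30 = 5.11, not 2.8.
- N = 100, the number in section 10.6.1: 10 × 2.80/√100 = 2.80.

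That mismatch is a separate matter. So is the use of 2.8 both as units on a 1-100 scale and as points on a 0-10 scale. Here the figure shows only that the plan targets a mean difference.

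**Does the count model fit the endpoint?** Inputs from the documents are 30 participants, months of 30 days, daily whole scores from 0 to 10, and entry pain of at least 2. Assumed for simulation: a mean level of 5 and a between-participant SD of 0.5 to 2.5.
- An average of 30 whole numbers is whole only when their sum is a multiple of 30, which happens about 1 time in 30 (3.3%). About 96.7% of averages are therefore not whole. Simulation gave 95-97%.
- With no effect, about 50% of changes are negative. With a 2.8-point effect on resveratrol only, nearly all resveratrol changes are negative, so pooled over both treatments the share is about (50% + 100%)/2 = 75%. Simulation gave 74-76%.
- A negative binomial distribution has probability 0 at 3.37 or at −1.4. One such observation makes the likelihood zero.

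**What if it is applied to raw daily scores?** These are non-negative whole numbers, so the model would run. Three problems remain.
- The outcome is then a daily score, not a change to a monthly average.
- The distribution has no upper limit, whereas the scale stops at 10.
- The direct estimates are a ratio of means and an odds for excess zeros. A ratio does not fix a difference: 2.8 points is a ratio of (4 − 2.8)/4 = 0.30 if the placebo mean is 4, and (6 − 2.8)/6 = 0.53 if it is 6 (both means assumed).

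**How likely is the zero trigger?** More than 30% of 30 means at least 10 participants. If each has probability p of counting as zero, the chance of 10 or more is:

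| p (assumed) | Chance of at least 10 of 30 |
|---|---|
| 10% | 0.0005 |
| 20% | 0.06 |
| 30% | 0.41 |

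Entry pain of at least 2 makes a large p unlikely. If zero refers to the monthly average, every day of the month must be 0, which makes it less likely still.

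**Does a rank difference identify points?** With 30 placebo and 30 resveratrol averages ranked together, the same 2.8-point effect gave these mean rank differences (the maximum possible is 30):

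| Between-participant SD (assumed) | Mean rank difference |
|---|---|
| 0.5 | 29.0 |
| 1 | 26.6 |
| 1.5 | 23.1 |
| 2.5 | 17.9 |

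One effect in points maps to many rank differences, depending on spread.

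**Does switching inflate type I error?** With 30 normal paired differences and Shapiro-Wilk at 5% as an assumed trigger, simulated error was 0.055 for the t-test alone and 0.057 with the switch. It was 0.066 if the better of the two tests were chosen, which the plan does not allow.

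**The case against.** The strongest reply is that these are fallbacks written in advance, not choices left open. The count branch has a numeric trigger and is reserved for an extreme case. Section 10.6.1 keeps analysts blinded to treatment. Section 10.1 also plans to compare mean and median monthly pain, so a description in points survives whichever branch is used. The word data in the count-model sentence may mean daily scores, and a difference in means could be derived from such a model.

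Most of this stands, and it rules out three stronger readings.
- A reader might infer that the method is picked to suit the results. The documents do not support that: both branches are pre-specified, the analysts are blinded, and the simulated inflation is negligible.
- A reader might infer that no estimate in points is possible under either branch. That is true of a model on ranks taken by itself. It is not strictly true of a count model on daily scores, although the plan specifies no conversion.
- A reader might infer that the rank branch will often be used. No rate can be given, because the plan names no test or variable. With Shapiro-Wilk at 5%, the entry floor of 2, 30-day averaging and assumed noise SDs of 1 to 1.5, change scores met the trigger in 5-8% of simulated trials and monthly averages in 5-23%.

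On the other side, section 10.5 allows for a placebo effect of about 20 on a 1-100 scale, roughly 2 points. Added to the hypothesised 2.8 points this makes about 4.8, so participants who enter near the floor could reach 0 if the drug worked that well. The count branch is therefore unlikely but not impossible.

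The reply does not rescue the count model for the endpoint as defined. The daily-score reading is not in the text, and it would replace the primary endpoint.

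**Conclusion.** The point holds in a limited form. The zero-inflated negative binomial rule is wrong as written for a change to a monthly average. This follows from the endpoint definition; the simulated shares only show how general the misfit is. Reading the rule as applying to daily scores changes the endpoint, ignores the upper limit of 10 and yields a ratio. The practical risk is small because the trigger is unlikely to be met with entry pain of 2 or more, but the documents give no figure from which to calculate that chance.

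The rank rule is a secondary gap. Its trigger is undefined, and a model on ranks does not itself estimate the hypothesised difference; only the descriptive comparison in section 10.1 stays in points. The consequence is an unclear primary estimate and avoidable analyst discretion, not a material rise in type I error. It should be corrected, and the correction is cheap.

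**What to change.** 1. Delete the negative binomial sentence from section 10.4.2.
2. State that the linear mixed model on the 0-10 scale, within the approach of section 10.4.1, gives the primary treatment difference in points with its confidence interval, whatever the distribution.
3. Name one robust inference method now and apply it unconditionally. Examples are a participant-level bootstrap stratified by sequence, or a randomisation test that permutes sequence labels across participants. It should not depend on a residual check, which would create another undefined switch. Labels should not be permuted within a sequence: everyone there has the same assignment, so the contrast would never change.
4. Report the rank analysis as a sensitivity analysis, naming the variable that is ranked.
5. If zeros are common, describe the share of zero-pain days by treatment.

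The cost is plan wording and a little programming, with no extra participants, visits or data. Power may be slightly lower than with ranks under heavy skew, which the sensitivity analysis would show. Bootstrap intervals can also be a little narrow with about 15 participants per sequence (30/2, assuming equal allocation), which is a reason to consider the randomisation test.

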#### 10.4.3 ANALYSIS OF THE SECONDARY ENDPOINT(S)

The data from the HRQoL instruments will be ascertained for each subject at the following time-points – prior to the start of the first period (first intervention), at 30 days after the start of the first period, at 60 days after the start of the first period, and at the end of the first period (90 days), at the start of the second period (second intervention) after the “washout” time of 30 days has passed, at 30 days after the start of the second period, at 60 days after the start of the second period, and finally at the end of the second period. These normalized scores will then be used in generalized mixed models as stated above. Baseline HRQoL will be compared to the 30, 60, 90 day HRQoL scores.

---

#### 10.4.4 SAFETY ANALYSES

The study DSMB will meet after every 10 patients have successfully completed the full study and all study data has been completed. The DSMB will be presented with all study-duration events (signs/symptoms/co-morbidities) that have been ascertained from all the patients that have completed their participation in the study and will be classified as study-related vs. incidental. The crude rate of the study-related event(s) will be tabulated with one-sided 95% confidence intervals. Additionally, for study-related events that occur in more than 5 patients will be further analyzed to incorporate duration of exposure to study drug.

---

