### 8.5 STUDY HALTING RULES

Administration of study agent will be halted study-wide when any of the following occur and are reported to the DSMB:

- three grade 3 AEs
- three grade 1 or grade 2 AEs of the same type
- three grade 1 or grade 2 AEs related to liver function
- one grade 4 or 5 AE

The research coordinator will notify the principal investigators and co-investigator immediately when the the study stopping criteria are met and enrollment screens will stop accepting new study participants. The principal investigator will inform the Data and Safety Monitoring Board (DSMB) members within 24 hours of this occurrence and will provide the DSMB with AE listing reports. The DSMB will convene an ad hoc meeting by teleconference or in writing as soon as possible. The DSMB will provide recommendations for proceeding with the study to the principal investigator. The principal investigator will inform the FDA of the temporary halt and the disposition of the study.

An individual participant will be asked to discontinue study medication if any of the following occur:

- one grade 3, 4, or 5 AE
- three grade 2 AEs
- five grade 1 AEs

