## 10.3 ANALYSIS DATASETS

The dataset analyzed will be comprise of demographic and clinical information obtained from the patient, the pain scores obtained from the pain and HRQoL instruments described above. The database will be maintained by the study coordinator and will be password-protected and stored on the secure and HIPAA-compliant University of Texas Health Science Center's zone 100 network. It will be accessible only to the study staff.

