##### 10.4.7.1 SAFETY REVIEW

The study DSMB will meet after every 10 patients have successfully completed the full study and all study data has been completed. Nonblinded information on all study-duration events (signs/symptoms/co-morbidities) that have been ascertained from all the patients will be classified as study-related vs. incidental.

---

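### Section 10.4.4, read literally, limits the tabulated adverse-event rates to patients who completed participation, so those who left early because of an event could be missing from them

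*Combined protocol and SAP*

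**What the plan says.** Section 10.4.4 is the only place that says how safety rates are formed. It opens with the timing: "The study DSMB will meet after every 10 patients have successfully completed the full study and all study data has been completed". The events shown are those "ascertained from all the patients that have completed their participation in the study". The next step follows directly: "The crude rate of the study-related event(s) will be tabulated with one-sided 95% confidence intervals". No numerator, denominator, interval method or direction is given. A further analysis is conditional on a count: "study-related events that occur in more than 5 patients will be further analyzed to incorporate duration of exposure to study drug".

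Section 10.4.7.1 repeats the timing but says that the events "ascertained from all the patients will be classified as study-related vs. incidental", with no restriction to completers.

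Section 10.3 is where a safety set would normally be defined. It describes data content only: "The dataset analyzed will be comprise of demographic and clinical information obtained from the patient".

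The plan provides for early exits caused by adverse events. Section 5.4.1 lets the investigator end participation for a clinical adverse event, and section 7.3.3 (day 90) removes a participant whose platelet count is below 50,000 per µl. Section 10.6.1 says that dropouts are not replaced.

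**The concern.** A patient taken out of the study because of an adverse event has not successfully completed it. If the rate is formed from completers, that patient leaves both the numerator and the denominator, and the event that says most about harm is the one not counted. The tabulated rate is the summary of safety that a reader of the final report will use. A one-sided interval, if its upper limit is the one meant, serves to show how large a rate the data still allow, and losing these patients lowers that limit.

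There is a second effect. The exposure analysis starts only when an event occurs in more than 5 patients. If early leavers are not counted, an event can pass that number among treated patients without being seen to do so.

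**Working it through.** The documents state no safety rate, bound or denominator, so there is no figure of the plan's own to reproduce. The check compares a completers-only set with a set of all treated participants.

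**Inputs from the documents**
- Number enrolled: 30 (section 10.5). Section 10.6.1 says one hundred; 30 is used here.
- Early leavers: 10% of 30 = 3 (the loss that section 10.6.1 says can be tolerated), and 33% of 30, about 10 (the attrition rate in section 10.5).

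**Assumptions**
- All 30 took at least one dose.
- The interval is an exact (Clopper-Pearson) upper limit; the plan names neither method nor direction.
- The numbers of leavers and completers with the event are not in the documents and are varied.

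**Formula.** For k patients with the event among n, the one-sided 95% upper bound is the 0.95 quantile of a Beta(k+1, n−k) distribution. For k = 0 this is 1 − 0.05^(1/n): 10.5% for n = 27, 9.5% for n = 30 and 13.9% for n = 20.

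| Leavers (with event) | Completers with event | Completers only: rate, bound | All 30: rate, bound |
|---|---|---|---|
| 3 (3) | 0 | 0/27 = 0%, 10.5% | 3/30 = 10.0%, 23.9% |
| 3 (3) | 3 | 3/27 = 11.1%, 26.3% | 6/30 = 20.0%, 35.7% |
| 10 (3) | 0 | 0/20 = 0%, 13.9% | 3/30 = 10.0%, 23.9% |
| 10 (0) | 0 | 0/20 = 0%, 13.9% | 0/30 = 0%, 9.5% |
| 10 (1) | 2 | 2/20 = 10.0%, 28.3% | 3/30 = 10.0%, 23.9% |

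**Direction.** Write c for completers with the event among n, and m for leavers with the event among d. The full rate (c+m)/(n+d) exceeds c/n exactly when m/d exceeds c/n. The completers' rate is therefore too low when the event is commoner among leavers than among completers. The bound also depends on the size of the set. In the last row the two rates are equal (1/10 among leavers, 2/20 among completers), yet the bound from 20 is higher than the bound from 30.

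Where only patients with the event are removed, so that k/n becomes (k−m)/(n−m), the bound fell in every case tried: n from 2 to 100, with at least one patient free of the event. That range includes an enrolment of one hundred.

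**The count of more than 5.** Four completers and two early leavers with the same event make 4 + 2 = 6, which starts the exposure analysis. Counting completers alone gives 4, which does not.

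**The case against.** The strongest reply is that completing the full study fixes only when the DSMB meets, while the set of patients is described in different words. Having completed participation may simply separate finished from ongoing patients and include those who finished early. Section 10.4.7.1 fits that reading, and the rate sentence names no denominator. This stands as a possible intention, so a reader should not infer that the plan has firmly chosen a completers' analysis. It does not settle the matter, because the literal wording differs between the two sections and nothing in section 10.3 decides between them.

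A reader might also infer that these events escape oversight. They do not. Section 8.3 records every event on study, section 8.4.1 informs the DSMB of all of them, section 8.4.2 sends it serious ones within 24 or 72 hours, and section 5.4.2 follows withdrawn participants for a month. The study-wide rules in section 8.5 would often act before the tabulation: five events of the same type meet one of them whatever the grades, and three do unless the grades are mixed. All this limits the consequence, but none of it defines the set behind the rates.

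Nor do the individual rules in section 8.5 by themselves exclude anyone. They begin "An individual participant will be asked to discontinue study medication if any of the following occur", which stops the product and not necessarily participation. The exits that matter are those in sections 5.4.1 and 7.3.3.

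Finally, it is tempting to say that the bounds will be too low. The last two rows of the table show that this is not certain.

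**Conclusion.** The point holds as a gap in definition with a possible bias. Followed literally, section 10.4.4 leaves out of the rates any participant whose participation ended early because of an adverse event, section 10.4.7.1 says otherwise, and no safety set decides between them.

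For the patients so removed the effect is downward: in the illustration the rate falls from 10.0% to 0% and the bound from 23.9% to 10.5%. The net effect over all leavers can go either way, since it depends on the share of leavers with the event, which the documents do not give. The sizes rest on the assumed counts, on 30 treated participants and on an exact upper limit.

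The plan should be changed because the restriction serves no stated purpose and the data needed for the full set are already to be collected.

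**What to change.** In section 10.4.4, replace the wording about patients who completed participation with: *all participants who took at least one dose, including those who stopped early*. Then:

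- Make that set the denominator of the final rates. At each DSMB review use all dosed participants who have finished or stopped early, and list events in ongoing participants separately, so that partly exposed patients do not dilute the rate.
- Tabulate crude rates by the product being taken at onset (resveratrol, placebo or washout). Someone who stopped in the first period never took the second product, so each column should count only those who entered that phase. State where events after an early last dose belong.
- Name the interval method and its direction.
- Use the same set in section 10.4.7.1.
- Keep exposure-adjusted rates as already planned, for events in more than 5 patients; the correction does not require them for every event.

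The cost is a few sentences and slightly more tabulation. Onset times (section 8.3) and events after withdrawal (section 5.4.2) are already collected. The date of the last dose is not listed for early stoppers and should be added to the form. No treatment, visit or sample size changes.
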